Infants must be enrolled in the prospective cohort study within 72 hours of birth. If the infant is older than 72 hours at the time of screening, s/he will be ineligible for the study.

Mother-infant pairs with the following traits will still be eligible for the study, given that no exclusion criteria are met.

Gestational age

As birthweight will be the main criteria for eligibility, we will enroll infants of any gestational age, as long as they meet the other inclusion criteria.

Multiples

Twins or triplets will be considered for enrollment in the study as multiples have higher rates of LBW and greater demands on a lactating woman. For the extension, they will still be considered as long as they are in the current prospective cohort. If only one infant in a multiple birth qualifies for inclusion, that infant may be enrolled and followed as a singleton would. If both infants qualify, both may be enrolled.

Maternal HIV Status

Women who are HIV infected are eligible. We will encourage the adherence to Option B+ standards so women are receiving HIV antiretroviral therapy in concordance with WHO and national guidelines.

Language

Mothers who do not speak English will still be eligible for the study.

Out-of-facility birth

Infants may be born anywhere and still be eligible for the study, as long as they present at a study facility for weight measurement within 72 hours of birth. See details below on identification and recruitment of these infants.

Prospective Cohort Extension study: This component will consist of enrolling mother/infant pairs.

Inclusion criteria for the mother/infant pair are:

- Currently enrolled in the LIFE study (follow-up from birth to 6 months of age) and fulfills all original inclusion criteria (infant birthweight between 1500g and <2500g, residence in catchment area of facilities in which born)
- Mother's and/or legally accepted representative (surrogate's) consent obtained for herself and infant for another 6 months of follow up

Exclusion criteria for the mother/infant pair are:

- Not previously enrolled in the LIFE study in addition to all original exclusion criteria (birthweight outside range, congenital abnormalities at birth, neonatal encephalopathy at birth, young mother, maternal death during labor and delivery, infant death before 72 hours of life, infant is more than 72 hours old at enrollment)

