9.18.2 Gestational age (baseline visit only)

Measuring gestational age is notoriously difficult. Prematurity and intrauterine growth restriction are the primary causes of LBW. We anticipate that there will be physiologic differences between these groups, but also acknowledge the challenges in accurate identification of gestational age in this study population due to limitations in prenatal care and use of early ultrasound. The availability and quality of gestational age data will be highly variable between study sites. Only one site (India-Karnataka site) will have access to early pregnancy ultrasonography, because of the presence of an existing trial for antenatal corticosteroid. In the remaining sites, the majority will likely not have access to ultrasound dating and will rely on last menstrual period (LMP) or Symphysis fundal height, as per standard of clinical care. We will capture what gestational age information is available from the woman's antenatal card, ultrasound history, etc. In cases where ultrasound data is available (either through clinic records or maternal self-report), we will consider this to be the first preference for gestational age dating. We will also ask the mother the date of her last menstrual period (LMP), and use this information as second preference for gestational age dating if ultrasound results are not available.

Given the poor quality and availability of antenatal dating in some sites, the LIFE study will also need to rely on neonatal assessment for gestational age dating. In a recent systematic review, 18 different neonatal assessments for gestational age dating were identified in the literature (Lee 2017). The most commonly used, simpler and feasible assessments, such as the Ballard or Capurro, were inaccurate, dating pregnancies to +/- 4 weeks of ultrasound dating. The Dubowitz exam was found to be the most accurate, dating 95% of pregnancies within +/- 2.6 weeks of an

ultrasound based date. However, the Dubowitz exam includes 21 signs including neurologic and external physical signs, and the feasibility of training, standardization and use in LMIC requires further programmatic research.

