9.20 Data analysis

As most of the quantitative data collected is being used for descriptive epidemiology of LBW infants, we will use means, medians and standard deviations to describe continuous variables. Categorical variables

will be analyzed with frequencies and proportions, as appropriate. Confidence intervals around all measures will be constructed to take any clustering into account.

For anthropometric analyses, we will use the INTERGROWTH charts to describe growth velocity and trajectories for the infants, including stunting (length-for-age z-score, LAZ), underweight (weight-for-age z-score, WAZ), and wasting (weight-for-length z-score, WLZ). To determine Z-scores, we will use the INTERGROWTH-21st standards for preterm infants (<37 weeks gestation), and the WHO postnatal growth standards for term infants (>37 weeks gestation) (Villar et al 2015).

Where possible, we will relate these anthropometric measures with reported infant feeding, using correlations for continuous variables or cross-tabulations of categorical variables. Any further analyses will be post-hoc and described separately.

6-month extension:

As with the original LIFE study, we will utilize mixed methods to fully understand the growth trajectories and care for LBW infants during the first 12 months of life. We will use the full cohort from 0 to 12 months of age to assess growth trajectories and velocities over time, evaluating the impact of complementary feeding (food types and timing) on infant anthropometrics, and assessing morbidities over time.

We will use descriptive methods for initial description of the LBW cohort with means, medians and standard deviations for continuous variables. Categorical variables will be analyzed with frequencies and proportions, as appropriate. Confidence intervals around all measures will be constructed to take any clustering into account.

For anthropometric analyses, for preterm infants we will use the INTERGROWTH-21st postnatal growth standards for preterm infants to describe growth velocity and trajectories for the infants up to 12 months of age, including stunting (length-for-age z-score, LAZ), underweight (weight-for-age z-score, WAZ), and wasting (weight-for-length z-score, WLZ). To determine Z-scores, we will use the INTERGROWTH-21st standards for preterm infants (<37 weeks gestation), and the WHO postnatal growth standards for term infants (>37 weeks gestation).

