We will use longitudinal multilevel models to assess the contribution of infant feeding and morbidity as well as maternal and household characteristics. Such models will also allow us to test whether there are differences in growth patterns related to gestational age and size for gestational age at birth, and whether the effects of care, feeding, and morbidity differ according to birth characteristics.

10 Qualitative research

As shown in Table 8, we will conduct FGDs and/or IDIs with a variety of stakeholders including clinicians, first-time and experienced mothers, family members, religious leaders, community leaders, traditional health care providers, supply chain and milk bank experts, and Ministry of Health officials. We might also speak with individuals that have been identified through the interviews as having a specific set of expertise or experience relating to the domains below. We recommend a minimum and maximum number of FGDs or IDIs for each of the populations that allows sites flexibility for religious leaders, community leaders, and traditional healers based on their context and which group is the most appropriate

to approach for these discussions. Each discussion will cover the domains listed – as well as others as they arise – corresponding directly to one or more of our study objectives.

Table 8: Focus groups and in-depth interviews, with domains for discussion

Focus group discussions	8-12 total	Domains for discussion	Meets objective		
			1	2	3
Mothers of preterm LBW infants aged 0-3 months	1				
Mothers of full-term LBW infants aged 0-3 months	1	Beliefs and norms around IYCF practices Feasibility and acceptability of IYCF options Preferences around IYCF support	✓	✓	
Mothers of preterm LBW infants aged 4-7 months	1	Barriers and facilitators to IYCF			
Mothers of full-term LBW infants aged 4-7 months	1				
Male family members of LBW infants	1-2	Beliefs and norms around IYCF practices Feasibility and acceptability of IYCF options	✓	✓	
Female family members of LBW infants	1-2	Role of family and community in IYCF practices			
Religious leaders		Beliefs and norms around IYCF practices Barriers and facilitators to IYCF implementation			
Community leaders	2-4	Feasibility and acceptability of IYCF options Religious and community leaders only: Role of religious or community leaders in IYCF Religious or community beliefs and rules around IYCF	✓	✓	
Traditional healers					

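### If the growth models use the planned z-scores, preterm-term differences in level cannot be told apart from the switch of growth reference at 37 weeks; the plan should name the outcome and use a common scale across that line

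*Combined protocol and SAP*

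**What the plan says.** The cohort mixes preterm and term infants by design: section 9.1 states that "we will enroll infants of any gestational age, as long as they meet the other inclusion criteria".

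Section 9.20 sets the growth scale. In the extension, the anthropometric analysis is "to describe growth velocity and trajectories for the infants up to 12 months of age, including stunting (length-for-age z-score, LAZ" and the corresponding weight-for-age and weight-for-length scores. The reference depends on gestational age at birth: "we will use the INTERGROWTH-21st standards for preterm infants (<37 weeks gestation), and the WHO postnatal growth standards for term infants (>37 weeks gestation").

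The last paragraph of section 9.20 then says: "We will use longitudinal multilevel models to assess the contribution of infant feeding and morbidity as well as maternal and household characteristics". The same models are to "test whether there are differences in growth patterns related to gestational age and size for gestational age at birth", and to examine "whether the effects of care, feeding, and morbidity differ according to birth characteristics". That paragraph names no dependent variable. Z-scores are the only growth scale that section 9.20 defines. The section gives no common reference, raw-scale outcome, separate preterm and term models, or sensitivity analysis on the reference.

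**The concern.** The reference is fixed entirely by which side of 37 weeks an infant falls on, and the models test a difference across that same line. A z-score measures distance from a reference median in units of that reference's SD. Two infants of identical size at the same age can therefore score differently because different references were applied to them. A preterm-term difference in mean z-score is the sum of any real difference and any gap between the references.

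This contrast matters to the study. Section 9.18.2 expects physiological differences between prematurity and growth restriction, and section 3 notes that complementary-feeding guidance is lacking for low-birthweight infants born at earlier gestational ages. An artefact at 37 weeks, or a real difference masked by one, would feed into that evidence.

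**Working it through.** The plan gives no figure to reproduce on this point. The check is structural, followed by an illustration.

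**1. Level contrast.** Let P = 1 for preterm infants and R = 1 for infants scored on INTERGROWTH-21st. Under the scoring rule P = R for every infant. A design matrix with intercept, P and R has rank 2 of 3. The coefficient on P estimates (true difference + d), where d is the gap between references. No sample size or covariate adjustment separates the two terms.

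**2. Slope contrast.** Write the gap at age t as d(t). A preterm infant's change from t1 to t2 carries d(t2) − d(t1).
- If d is constant, this is zero and the preterm-term slope difference is unbiased.
- If d(t) = d0 + d1·t, the slope difference is biased by d1.

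**3. Interaction with feeding or morbidity.** Within preterm infants at a given age, (fed + d) − (not fed + d) = fed − not fed, so a gap common to both feeding groups cancels. Two routes to distortion remain.
- SD units: a raw effect b becomes b/S1 on one reference and b/S2 on the other, so equal raw effects look unequal if S1 ≠ S2.
- Age-dependence: if d varies with age and feeding exposure also varies with age, the gap no longer cancels.

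**4. Contrasts on one side of 37 weeks.** These use one reference, so d does not enter. This covers gestational-age slopes and size-for-gestational-age contrasts within the preterm group or within the term group. A model with continuous gestational age plus a reference indicator has full rank (3 of 3).

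**5. Illustration for a level difference at one time point.** Inputs:
- 300 per site: the expected final sample of mothers in section 9.12. Sites are analysed separately under section 2.1.
- Half preterm, z-score SD 1.1, two-sided 5% test, and the gaps: assumed, because the documents give none of these.

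SE = 1.1 × √(1/150 + 1/150) = 0.127

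Chance of p<0.05 with no true difference = Φ(d/SE − 1.96) + Φ(−d/SE − 1.96)

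| Gap d (z) | d/SE | Chance of p<0.05 |
|---|---|---|
| 0 | 0 | 5% |
| 0.1 | 0.79 | 12% |
| 0.2 | 1.57 | 35% |
| 0.3 | 2.36 | 66% |
| 0.5 | 3.94 | 98% |

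With SD 1.0 (SE 0.115), the values for 0.1 to 0.5 z are 14%, 41%, 74% and 99%. With 30% preterm and SD 1.1, SE = 1.1 × √(1/90 + 1/210) = 0.139 and they are 11%, 30%, 58% and 95%.

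**6. Gestational age as one linear term, with no reference indicator.** Assume gestational age is uniform over whole weeks 32 to 41, with week 37 scored as term (the plan assigns exactly 37 weeks to neither reference). The covariance of gestational age with P is 0.5 × 34 − 36.5 × 0.5 = −1.25, and the variance is 8.25. The spurious slope is d × (−1.25/8.25) = −0.15d per week: −0.015 z per week at d = 0.1 and −0.076 at d = 0.5.

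**The case against.** The strongest objection is that the models may not use z-scores at all. The paragraph names no outcome, and section 9.18.3 collects weight, length, head circumference and mid-upper arm circumference. If raw measures are modelled, the problem does not arise. This stands as a limit on the point. It also shows the gap: a plan that tests across 37 weeks should say on what scale.

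A reader might infer that every gestational-age result, every growth slope and every feeding interaction is compromised. The documents do not support that. Growth patterns in a longitudinal model most naturally mean trajectories, and a constant gap cancels from slopes and interactions (steps 2 and 3). Nothing in the documents shows that the gap varies with age or that the SD units differ. Contrasts within each group, including size for gestational age, are untouched.

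A reader might also take the percentages as an estimate of how often the study would mislead. They are not. The gaps are assumed, zero is among them, and the figures apply only to a level difference at one time point.

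Section 9.12 says no hypothesis tests are planned, so a 5% criterion is not the plan's own. But section 9.20 does say the models will test these differences, and an estimate with a confidence interval would carry the same bias.

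Finally, a common scale at corrected age has its own weakness. It leans on gestational-age dating, and the Dubowitz exam is described as "dating 95% of pregnancies within +/- 2.6 weeks of an" ultrasound-based date. It also compares infants at different times since birth. Both objections stand and belong in the statement of the result.

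**Conclusion.** The point holds in a limited form. On the natural reading of section 9.20, where z-scores are the only growth scale defined, a preterm-term difference in level is completely confounded with the choice of reference, and nothing elsewhere in the documents repairs this. Slopes and interactions across 37 weeks are at risk only if the gap between references changes with age or their SD units differ. Comparisons within the preterm group or within the term group are sound in this respect.

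The direction and size of any distortion cannot be derived from the documents; the table in the working shows only how the risk grows with an assumed gap. The descriptive aims are unaffected. The change should be made because the test as written could not be interpreted if the outcome is the two-reference z-score.

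**What to change.** 1. Keep the two-reference z-scores for describing stunting, underweight and wasting.
2. Name the dependent variable in the multilevel-model paragraph of section 9.20.
3. For any contrast or interaction across 37 weeks, use a common scale: raw weight and length modelled against corrected age, or one reference at corrected age for all infants at the ages it covers.
4. Report the two-reference z-score result for the same contrast as a sensitivity analysis.
5. State the age scale with each result, since corrected age depends on dating and compares infants at different times since birth.

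The cost is analysis-plan wording and some extra modelling. Weight, length and gestational age are already collected (sections 9.14, 9.18.2 and 9.18.3), so no new data are needed. Dating error remains, but on the common scale it would no longer also switch an infant from one reference to the other.

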10.1 Focus group eligibility criteria

Mothers

These four focus groups will include mothers of LBW infants only. Two groups will include mothers of LBW infants aged 0-3 months, and two for mothers of LBW infants aged 4-7 months. The groups will be further stratified by preterm and full-term infants.

Mothers with healthy birthweight infants or VLBW infants will be excluded. Mothers with HIV will be eligible for participation. Mothers under the age of 18 will be excluded in India and Tanzania, and unmarried mothers under the age of 16 will be excluded in Malawi.

Mothers' participation in the prospective and observational studies will not impact their eligibility for participation in the focus group discussions. Should sites find it difficult to recruit mothers for focus group discussions then they will be able to conduct individual interviews instead.

Mother's family members

Family members with the following relationship to a mother of a LBW infant up to 7 months old are eligible to participate: husbands, guardians, mother's parents, mother's in-laws, grandmothers, sisters, and sisters-in-law. The focus groups will be separated by gender: fathers, husbands, and grandfathers in their own group, and sisters, sisters-in-law, and grandmothers in a separate group. In India, the female focus groups will be further separated into family members from the mother's generation (sisters, sisters in law) and those from the older generation (mothers-in-law, grandmothers.)

To be eligible, relatives must play a role in providing opinions, care, or support for the mother related to IYCF. Eligible family members do not need to be family members of the participating mothers in the project; they only need to be family members of a current mother with a LBW infant. Family members are eligible to participate even if the mother has died or if the mother is not participating in the focus groups, observation, or prospective components of the study.

Religious leaders, community leaders, or traditional healers

The aim of these focus groups is to capture the social norms and pressures on breastfeeding behavior in the community beyond women's immediate families. The intent is that the three categories of people can inform the study of religious, social, and naturopathic norms in each site.

For each focus group, sites can decide the best composition for the group. For example, the FGDs can be segregated by role (i.e. only religious leaders in a single group) or by gender (i.e. female community leaders and female traditional healers in a single group), but the compositions are not limited to these options. While both men and women will be eligible for these focus groups, they need not be separated by gender. All sites will conduct between 2-4 FGDs and determine which roles are appropriate to participate in focus groups based on what is relevant for that context.

Religious leaders will be eligible if they are recognized leaders of the community's primary religion(s). Community leaders or elders will be eligible if they are viewed as opinion leaders or having significant influence over IYCF practices in the area. Traditional healers are those in the community who provide non-Western medical care, and these individuals will be eligible for participation if they provide care directly to mothers or infants related to IYCF practices, or advise other people who carry out, support, or influence infant feeding.

Health care workers

Health care workers who are currently involved in providing support for IYCF will be eligible. They must either provide care directly to mothers or infants, provide advice to people who feed or support/influence feeding, or support or supervise other clinicians that directly provide care to mothers or infants. Health care workers who could be involved in the future in providing support for IYCF will also be eligible. Examples of healthcare workers include nurses, nurse midwives, and midwives. We will exclude health care workers who have been at their position for less than six months

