8.3 Inclusion/exclusion criteria

Inclusion criteria for the mother/infant pair for in-facility observations are:

Infant birthweight between 1500 and <2500 g

We will use the facility-based birthweight taken at the time of delivery for the eligibility checklist.

Mother's consent

Only women who give written consent at the time of birth will be included.

Exclusion criteria for the mother/infant pair are:

Infant very low birthweight

Children who are very low birthweight (<1500g) will have different clinical needs and interventions. Thus, these infants will be excluded.

Congenital abnormality that interferes with feeding

Infants will be excluded if they have a congenital abnormality that (1) directly interferes with feeding and (2) is readily apparent at birth, requiring no special diagnostic tools. The specific abnormalities for exclusion are:

- Cleft lip or palate
- Hydrocephalus

- Gastrointestinal tract anomalies including gastroschisis, omphalocele, or anal atresia
- Neural tube defects
- Congenital cardiac defects
- Suspected Trisomy 21
- Suspected TORCH infection such as congenital rubella, CMV, toxoplasmosis, or syphilis.

Young mother

In Tanzania and India, women under 18 will be excluded.

In Malawi, women aged 16 to 17 who are married are considered legally emancipated and able to give independent consent, so they may participate. Women who are 16 to 17 and are unmarried will be excluded. All women and girls under 16 will be excluded.

Infant death

If the infant dies within the screening window for observation enrollment (within 6 hours after birth) before the mother can be approached for consent, the mother-infant pair will be excluded. We will also exclude infants that are part of multiple births where the other baby(ies) have died (even if the surviving infant is otherwise eligible).

Maternal death

The study will exclude cases of maternal death that occur during labor and delivery or within the 6-hour post delivery enrollment period.

Out-of-facility birth

Infants born outside of the facility cannot be observed at birth.

Infant >6 hours old at screening

Infants must be enrolled in the in-facility observation study within 6 hours of birth. If the infant is older than 6 hours at the time of screening, s/he will be ineligible for the study.

Mother-infant pairs with the following traits will still be eligible for the study, given that no exclusion criteria are met.

Critical or severe illness jeopardizing early survival

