Some infants with other seriously life-threatening illnesses may not be diagnosed in the early hours and days. This is because some conditions require expensive or invasive diagnostic tests, and others, such as sepsis, may be undetectable for a period of time. If these infants meet all other criteria, then they would be enrolled in the prospective cohort even though they are at higher risk of mortality. Most of these cases will die before 72 hours, since neonatal mortality is concentrated early. In those cases we will replace the infant in the cohort sample. (See section below on “replacement of infants who die in the first 72 hours.”)

Plans to leave the study area before end of data collection

In order to conduct the study, we will need to be able to follow mother-infant pairs. If a mother-infant pair plans to leave the study area within 6 months, per maternal self-report, they will not be enrolled. As part of the study set up, we will seek additional insight from local partners on practices of returning to maternal home for birth of child.

Young mother

In Tanzania and India, women under 18 will be excluded.

In Malawi, women aged 16 to 17 who are married are considered legally emancipated and able to give independent consent, so they may participate. Women who are 16 to 17 and are unmarried will be excluded. All women and girls under 16 will be excluded.

Maternal death

The study will exclude cases of maternal death that occur during labor and delivery (or at any time before the consenting process would begin for this study.) Although the LBW infants of deceased mothers are particularly vulnerable and important to study, we anticipate very few, if any, maternal deaths in samples of roughly 300 in each site. Also, given the logistical and ethical complexity in recruiting and following these cases, they would likely require separate study processes, which would take effort and scarce study resources to prepare for, even if no deaths occur.

Maternal deaths will count as an exclusion criteria for the prospective cohort if they occur before enrollment. In the event that a mother dies at any time after enrollment, the infant will still be retained in the cohort.

Infant death

The study will exclude infants that die before enrollment can occur, as well as infants that are part of multiple births where the other baby(ies) have died (even if the surviving infant is otherwise eligible).

Infant >72 hours old at screening

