10.5 Informed consent

The study team will obtain written informed consent from all participants before the start of the interview or focus group discussion.

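### As written, the Malawi focus-group age rule in section 10.1 admits unmarried 16-17 year olds and married girls under 16, whom sections 8.3 and 9.1 exclude from the observations and the cohort

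*Combined protocol and SAP*

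**What the plan says.** The protocol states an age rule for mothers in three places.

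- **Section 8.3 (in-facility observations)** has a three-part rule for Malawi. First: "In Malawi, women aged 16 to 17 who are married are considered legally emancipated and able to give independent consent, so they may participate". Second: "Women who are 16 to 17 and are unmarried will be excluded". Third: "All women and girls under 16 will be excluded".
- **Section 9.1 (prospective cohort)** repeats that rule, with the same consent reason for married 16-17 year olds and the same two exclusions: "Women who are 16 to 17 and are unmarried will be excluded. All women and girls under 16 will be excluded".
- **Section 10.1 (mothers' focus groups)** has one clause for Malawi: "unmarried mothers under the age of 16 will be excluded in Malawi". For the other two countries it says "Mothers under the age of 18 will be excluded in India and Tanzania", which agrees with 8.3 and 9.1.

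Two further statements decide whether the stricter rule reaches the focus groups by another route. Section 10.1 says that taking part in the cohort or the observations "will not impact their eligibility for participation in the focus group discussions". On consent, section 10.5 consists of one sentence: "The study team will obtain written informed consent from all participants before the start of the interview or focus group discussion".

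**The concern.** In 8.3 and 9.1 the Malawi rule for 16-17 year olds turns on whether the young woman can consent for herself. Marriage is what makes the 16-17 year old eligible, and the unmarried 16-17 year old is left out. Section 10.1 drops the 16-17 band and makes marital status a condition of the under-16 exclusion. An unmarried 17 year old, or a married 15 year old, would then pass the focus-group criteria in Malawi although the cohort and the observations would turn her away.

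What is at stake is participant protection. The protocol could bring minors into a group discussion on their own signature when its own reasoning, at least for the unmarried 16-17 year olds, implies that this signature is not enough. The setting is low risk but not free of risk: section 10.9 accepts that participants may be judged by others in the group and that confidentiality between members cannot be guaranteed. Field staff will apply the sentence as written, and ethics committees will have approved it as written.

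**Working it through.** No sample-size, power or precision figure is involved, so the check is a comparison of the rules, followed by a count of the people the focus-group rule governs.

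**Step 1. Compare the rules over every combination of age and marital status in Malawi.**

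| Age | Marital status | Sections 8.3 and 9.1 | Section 10.1 as written | Agree? |
|---|---|---|---|---|
| Under 16 | Unmarried | Excluded | Excluded | Yes |
| Under 16 | Married | Excluded | Not excluded | **No** |
| 16-17 | Unmarried | Excluded | Not excluded | **No** |
| 16-17 | Married | Eligible | Eligible | Yes |
| 18 and over | Unmarried | Eligible | Eligible | Yes |
| 18 and over | Married | Eligible | Eligible | Yes |

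Two of the six combinations conflict. In both, the focus-group rule is the looser one.

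**Step 2. Look for anything that closes the gap.**

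- *Carry-over from another component.* None. Section 10.1 separates focus-group eligibility from participation in the cohort and the observations.
- *Screening at recruitment.* Section 10.4 has study staff approach mothers at the facility, before discharge or at a postnatal visit. It describes no check of age or marital status.
- *Consent procedure.* Section 10.5 asks for written consent from every participant and does not say who signs for a minor.
- *Other text in section 10.* Nothing there restates or corrects the Malawi rule.

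**Step 3. Set the scope.**

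- Section 10.1 allows individual interviews in place of mothers' focus groups where recruitment is difficult. The same rule would govern those.
- The extension interviews are not affected. Section 10.3 draws those mothers from the cohort, where the 9.1 rule already applies.
- The chart review (section 11.1.1) takes its young-mother exclusion from 8.3, and the extension cohort keeps the one in 9.1. Section 10.1 is the only outlier.

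**Step 4. Count the mothers recruited under the rule.** Tables 2 and 8 plan four mother groups per site, and Table 2 gives 5-8 participants per group:

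- lower end: 4 × 5 = 20
- upper end: 4 × 8 = 32

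The documents do not give the share of Malawian mothers of low-birthweight infants who are under 18, or their marital status. The number in the two conflicting rows therefore cannot be calculated. It lies between 0 and the group total.

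**The case against.** The best defence is that section 5 says each activity has its own eligibility criteria and consent process, so a focus-group rule that differs from the cohort rule is not in itself an error. This stands as far as it goes: 8.3 and 9.1 exclude these young women from two components, not from the study as a whole. It does not explain the difference. Legal capacity to consent would not normally change with the activity, section 10.1 gives no reason, and its rule for India and Tanzania is the same as elsewhere. A faulty compression of the three-part rule is the likelier explanation, but the compressed sentence is what staff would apply.

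A reader might also infer four stronger things, none of which the documents support.

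- *That the protocol declares both groups incapable of consenting.* Its consent reason is attached only to admitting married 16-17 year olds. For unmarried 16-17 year olds the converse is a fair inference. For girls under 16, married or not, no reason is stated, and the position in Malawian law is not in the documents.
- *That there is no parental-consent process.* Section 10.5 describes none. The consent forms were not in the copy reviewed, so a guardian or assent form may exist.
- *That the affected discussions would be unusable.* Nothing in the protocol says what happens to group data after an ineligible enrolment.
- *That 20 to 32 minors are exposed.* That is every mother in the Malawi groups, most or all of whom may be adults.

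**Conclusion.** The inconsistency is real. Read as written, section 10.1 makes two categories of minor eligible for the Malawi mothers' focus groups, and for interviews replacing them, that 8.3 and 9.1 exclude from the observations and the cohort. Nothing elsewhere in section 10 corrects it. Because it concerns the eligibility of minors, it should be put right even though it is one sentence in a non-interventional component.

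Its practical size is small and unknown: up to four groups recruited under the rule, with possibly no one in the conflicting categories. Sample size, estimates and confidence intervals are unaffected.

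The conclusion rests on reading unmarried and under 16 as joint conditions, which is the plain sense of the sentence. The consent argument carries most weight for unmarried 16-17 year olds. For married girls under 16 the finding is a conflict between sections, without a stated ground.

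**What to change.** Replace the Malawi clause in section 10.1 with the rule already in 8.3 and 9.1: exclude everyone under 16, exclude unmarried women aged 16-17, and allow married women aged 16-17. A cross-reference to 8.3 would do this and prevent further drift. Make the same change in the recruitment checklist for the mothers' groups and for any interviews that replace them.

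If the wider rule was intended, section 10.1 should say why it differs, and section 10.5 should set out the consent route for these minors.

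If any Malawi mother groups have already been held, compare participants' recorded age and marital status, where available, with the 8.3 and 9.1 rule.

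The cost is one sentence and a checklist edit, submitted as a minor amendment. No analysis, sample size or timeline is touched.
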